1.2.2.3 Clinical Studies in Children

Not applicable, only patients aged 18-64 will be recruited for this study.

1.3 Selection of Drugs and Dosages

Lidocaine (NDC 0338-0411-02) will be dosed at 2 mg/kg and given intravenously over 5 minutes. Hydromorphone (NDC 0409-1283-31) will be given at a dose of 1 mg, intravenously over 5 minutes. These are the maximum daily doses for each medication under this protocol,

however more hydromorphone can be given at the discretion of the treating provider if the patient has insufficient analgesia.

1.4 Compliance Statement

This study will be conducted in full accordance of all applicable Hennepin Healthcare Research Policies and Procedures and all applicable Federal and State laws and regulations. All episodes of noncompliance will be documented and reported according to the Prompt Reporting Guidelines, Attachment EEE, of the Hennepin Healthcare IRB Policies and Procedures.

The investigators will perform the study in accordance with this protocol, will obtain consent and assent, unless waiver of consent or other alteration is approved, and will report unanticipated problems involving risks to subjects or others and SAEs in accordance with The Hennepin Healthcare IRB Policies and Procedures and all Federal requirements. Collection, recording, and reporting of data will be accurate and will ensure the privacy, health, and welfare of research subjects during and after the study.

2 STUDY OBJECTIVES

The overall objective of this study is to determine if intravenous lidocaine can have equal analgesic efficacy as hydromorphone while having an equal safety profile in patients with acute abdominal pain.

2.1 Primary Objective (or Aim)

The primary objective of this study is to determine whether intravenous lidocaine dosed at 2 mg/kg has equal analgesic efficacy as intravenous hydromorphone at 1 mg, as measured by the improvement in pain score after 90 minutes following administration of study drug.

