Attachment UUU

**High Dose IV Lidocaine vs Hydromorphone for Abdominal Pain in the Emergency
Department (HIDO-LIDO)**

NCT = NCT04398316

Document Date = 7/21/2020

Title: **High DOse Intravenous LIDOcaine vs Hydromorphone for Acute Abdominal Pain in the Emergency Department: A Prospective, Blinded, Randomized, Comparative Efficacy Trial (HIDO-LIDO)**

Drug or Device Name(s): Lidocaine

FDA IND/IDE 151174

Sponsor: [name]

Protocol Date: 5/27/2020

Revision Date(s): 6/25/2020
6/23/2020
7/21/2020

[name]:
Hennepin Healthcare
Department of Emergency Medicine, R2
[name]
[contact]
email: [contact]

[figure not shown]
PROTOCOL SYNOPSIS

Study Title	High DOse Intravenous LIDOcaine vs Hydromorphone for Acute Abdominal Pain in the Emergency Department: A Prospective, Blinded, Randomized, Comparative Efficacy Trial (HIDO-LIDO)
Funder	Department of Emergency Medicine
Clinical Phase	Phase IV
Study Rationale	The rationale for this study is to find an alternative to opioids for treating acute pain in the emergency department. In a subgroup analysis of a recently published study, intravenous lidocaine at a dose of 2 mg/kg had equivalent efficacy for acute abdominal pain compared to 1 mg of hydromorphone, thus warranting further investigation with a prospective, randomized clinical trial (14).
Study Objective(s)	Primary 
• To determine the analgesic efficacy of intravenous lidocaine dosed at 2 mg/kg for acute abdominal pain in the emergency department, as compared to a single 1 mg dose of hydromorphone. Secondary 
• To compare the safety of intravenous lidocaine dosed at 2 mg/kg compared to a single 1 mg dose of hydromorphone.
Test Article(s) (If Applicable)	Lidocaine, administered intravenously at a dose of 2 mg/kg, over 5 minutes. Hydromorphone, administered intravenously at a dose of 1 mg, over 5 minutes.
Study Design	This will be a prospective, randomized, double blinded, comparative efficacy trial.
Subject Population Key Criteria for Inclusion and Exclusion:	Patients aged 18-64 presenting to the emergency department with severe (defined as requiring an intravenous opiate) acute (defined as duration of 7 days or less) abdominal pain (anywhere on the abdomen or flank).
Number Of Subjects	Total Number of Subjects: 187 Total Number at Hennepin Healthcare: 187 Total Number of Sites: 1

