3 INVESTIGATIONAL PLAN

3.1 General Schema of Study Design

Patients presenting to the emergency department with abdominal pain will be screened for eligibility. Once deemed eligible, they will be randomized to receive either intravenous lidocaine or hydromorphone. The patient, ED nurse and physician will all be blinded to the study drug. Only the research pharmacist will know the drug that the patient is receiving. Primary and secondary endpoints will be measured from the time just before the patient receives the study drug and for the next 180 minutes then once again 7 days later (please refer to Table 1 for timing and specific data being measured). The two drugs will then be compared against one another.

Much of each patient's care will be "standard of care", most likely to include intravenous access, venipuncture, labs, imaging, and potentially consultations by other services. Please refer to Figure 1 for an illustration of study interventions. Standard care can take place at anytime on Figure 1.

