6 STATISTICAL CONSIDERATIONS

6.1 Primary Endpoint

The primary endpoint is mean improvement in pain score, defined as the difference between pain score at the beginning of the study drug infusion (time zero) and 90 minutes after the study drug was administered (time zero). The mean pain improvement will be compared between each study drug using a two tailed t-test with an alpha level of 0.05 and confidence interval.

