6.2.2 Efficacy Analysis

The primary outcome will be assessed using a two-tailed t-test using an alpha level of 0.05. A 95% confidence interval will be recorded for each mean. The same test will be used for all numerical pain outcomes. All other tests will use a chi-square test with an alpha level of 0.05 and confidence interval of 95%.

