9.4.4 Risk-Benefit Assessment

As stated above, there are minimal risks for participating in this study. While patients will not directly benefit from participating in this study, future patients can benefit if lidocaine has equal analgesic efficacy as hydromorphone. Essentially, it would minimize the need for narcotics to treat acute abdominal pain in the emergency department.

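### The primary objective asks whether lidocaine is equal to hydromorphone, but the planned test of difference can refute equality and cannot support it

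*Combined protocol and SAP*

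**What the plan says.** Three places in the protocol frame the trial around equality. Section 2 gives the overall objective as to "determine if intravenous lidocaine can have equal analgesic efficacy as hydromorphone while having an equal safety profile". Section 2.1 gives the primary objective as "to determine whether intravenous lidocaine dosed at 2 mg/kg has equal analgesic efficacy as intravenous hydromorphone at 1 mg", measured by pain improvement at 90 minutes. Section 9.4.4 rests the value of the trial on a positive answer: "future patients can benefit if lidocaine has equal analgesic efficacy as hydromorphone".

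Other places are neutral. The synopsis words the primary objective as efficacy "as compared to a single 1 mg dose of hydromorphone", and section 3.1 says "The two drugs will then be compared against one another".

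The analysis follows the neutral wording. Under section 6.1, mean improvement is "compared between each study drug using a two tailed t-test with an alpha level of 0.05 and confidence interval". Section 6.2.2 repeats the test and adds: "A 95% confidence interval will be recorded for each mean". The sample size in section 6.3 is for detecting a difference of 1.3 points, and the interim efficacy boundary in section 6.4 is also a test of difference. Nowhere is there an equivalence or non-inferiority margin, a limit against which an interval is read, or an interpretation of p>0.05.

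**The concern.** A test of no difference gives an asymmetric answer to the question in section 2.1. If p is at or below 0.05, equality is refuted. If p is above 0.05, the data may be compatible both with no difference and with a difference that the protocol itself regards as important. The plan therefore has a rule for *no* and none for *yes*, although section 9.4.4 depends on *yes*.

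The confidence intervals do not close the gap. The one in section 6.1 is most naturally for the comparison, but it has no limit to be read against. The ones in section 6.2.2 are for each arm mean and do not directly bound the difference.

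No section says that p>0.05 will be called equality. The protocol has, however, already used such language for the earlier trial's 2 mg/kg subgroup. The synopsis says it "had equivalent efficacy for acute abdominal pain compared to 1 mg of hydromorphone", section 1.2 calls its 5-point improvement equal to that with hydromorphone, and section 1.2.2.2 calls it equally efficacious. None of these gives an interval or a margin. At stake is whether an inconclusive trial is reported as support for replacing an opioid.

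**Working it through.** **Inputs (section 6.3 unless stated).** SD 3; important difference 1.3; two-sided alpha 0.05; power 80%; 85 per arm; 10% loss; total 187. Section 1.2 gives the earlier trial's improvements as 3.8 and 5, a gap of 5 − 3.8 = 1.2. The deficit is hydromorphone minus lidocaine in mean improvement.

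**The plan's own figure.** The t-test sample size for 1.3 with SD 3 is 84.6, so 85 per arm, with power 80.2%. For the total, 170 × 1.10 = 187. The stated size reproduces, and it belongs to a test of difference.

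**Precision at 85 per arm.**
- SE = 3 × √(2/85) = 0.460.
- Half-width of the 95% interval = 1.974 × 0.460 = 0.908.
- p>0.05 when the observed difference, in either direction, is below 0.908.
- The interval includes a 1.3 deficit when the observed deficit is at least 1.3 − 0.908 = 0.392.
- So an observed deficit from 0.39 to 0.91 is non-significant and also fails to exclude 1.3.

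**Example.** Observed deficit 0.65: t = 0.65/0.460 = 1.41, p = 0.16, 95% interval −0.26 to 1.56.

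**How often this happens (noncentral t; simulation of 2,000,000 trials for the joint figure at 0.5).**

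| True lidocaine deficit | P(p>0.05) | P(p>0.05 and interval includes 1.3) |
|---|---|---|
| 0 | 0.95 | 0.173 |
| 0.5 | 0.81 | 0.40 |
| 1.2 | 0.263 | 0.222 |

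At a true deficit of 0, the upper limit is below 1.3 with probability 0.802. That includes 0.025 in which lidocaine is significantly better, so the joint figure is 0.95 − (0.802 − 0.025) = 0.173. At 1.2, power is 0.737 and the upper limit falls below 1.3 with probability 0.041, so the joint figure is 0.263 − 0.041 = 0.222.

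**Sensitivity to the analysed number.** Section 3.3.2 stops recruitment at 187 consented. A 10% loss leaves 187 × 0.9 = 168.3, about 84 per arm. Then SE = 0.463, half-width 0.914, range 0.386 to 0.914, and power at 1.3 is 79.7%. Nothing material changes.

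**If a non-inferiority claim were wanted.** The documents give no margin, so the margins here are assumptions. One-sided alpha 0.025, SD 3, true difference 0:

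| Margin | Power at 85 per arm | Per arm for 80% power |
|---|---|---|
| 1.3 | 80% | 85 |
| 1.2 | 74% | 100 |
| 1.0 | 58% | 143 |

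**The case against.** The strongest reply is that this is a coherent difference trial with one loose word. The title, synopsis, section 3.1 and all of section 6 describe a comparison with reproducible power for a stated important difference. Section 6.1 plans an interval and section 6.3 supplies 1.3, so all that is missing is a sentence joining them. The harm is only a possible later misreading. It can also be said that the 26% chance of p>0.05 at a true deficit of 1.2 is ordinary type II error, and that the 1.2 gap came from a fixed 120 mg dose rather than 2 mg/kg.

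Much of this is true. The sample size is not at fault, and the 1.2 gap is an illustration, not a threshold set by the protocol. But *equal* stands in the formal objectives and in the benefit statement, and the missing sentence is the one that decides what the trial may conclude. Ordinary type II error is exactly why p>0.05 cannot answer *yes*.

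Two further points are fair. First, using 1.3 as a reading limit could act as an unjustified margin. The fix therefore reports the limit and does not allow the word *equal*. Second, the 17% counts deficits only. By symmetry, if the drugs are truly equal, about 2 × 17.3% = 35% of trials are non-significant and fail to exclude 1.3 in one direction or the other. Rescue analgesia could also bring the arms closer together; its handling is a separate question that this fix does not settle.

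**Conclusion.** The concern holds and must be fixed before data are seen. As written, the plan can answer its primary question negatively but has no route to the affirmative answer on which section 9.4.4 relies. The ambiguous zone is an observed lidocaine deficit of 0.39 to 0.91 points. A trial falls in it with probability 17% if the drugs are equal, about 40% if lidocaine is worse by 0.5, and 22% if it is worse by 1.2. These figures assume SD 3 in both arms, 85 analysed per arm and normally distributed means. They take 1.3 as the relevant difference because section 6.3 does. That the objective and the test do not match depends on none of these numbers.

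**What to change.** In sections 6.1 and 6.2.2, make the two-sided 95% confidence interval for the between-arm difference in mean improvement at 90 minutes (hydromorphone minus lidocaine) the basis for interpretation, and state that:

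1. p>0.05 alone is not evidence of equal efficacy;
2. a non-significant result whose interval includes a 1.3-point deficit is inconclusive;
3. a non-significant result whose upper limit is below 1.3 is reported as excluding a deficit of 1.3 or more, with the limit shown, and is not called equal.

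Reword sections 2 and 2.1 to estimate and compare the difference, in line with the synopsis, and bring section 9.4.4 into agreement. For safety, sections 6.2 and 6.2.2 already plan a difference in proportions and a 95% interval. Add only that a non-significant chi-square test does not show an equal safety profile.

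This changes wording only: same test, same 187 patients, sections 6.3 and 6.4 untouched. The price is that some non-significant results must be reported as inconclusive, at the rates given above.

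If the sponsor wants an affirmative claim, the objective should instead be restated as non-inferiority with a prespecified, justified margin. That has a cost. A margin of 1.3 keeps about 80% power at 85 per arm but exceeds the 1.2-point gap that section 1.2 describes as lidocaine not doing as well. Smaller margins need more patients, as tabulated above, and the difference-based efficacy boundary in section 6.4 would need review.

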2.2 Secondary Objectives (or Aim)

The secondary objectives are to:

- Measure improvement in pain at 15 minutes, 30 minutes, 60 minutes, 120 minutes, 150 minutes and 180 minutes following administration of study drug.
- Measure frequency of sufficient pain relief, defined as no need for pain medication outside of investigational drug.
- Measure the safety of lidocaine, as determined by comparing its rate of side effects, frequency of medication administration required to treat side effects, the frequency of serious adverse events, disposition change attributed to study drug, and frequency of missed diagnosis to hydromorphone.
- To measure patient preference for the study drug they received (would they want it again).

3 INVESTIGATIONAL PLAN

3.1 General Schema of Study Design

Patients presenting to the emergency department with abdominal pain will be screened for eligibility. Once deemed eligible, they will be randomized to receive either intravenous lidocaine or hydromorphone. The patient, ED nurse and physician will all be blinded to the study drug. Only the research pharmacist will know the drug that the patient is receiving. Primary and secondary endpoints will be measured from the time just before the patient receives the study drug and for the next 180 minutes then once again 7 days later (please refer to Table 1 for timing and specific data being measured). The two drugs will then be compared against one another.

Much of each patient's care will be "standard of care", most likely to include intravenous access, venipuncture, labs, imaging, and potentially consultations by other services. Please refer to Figure 1 for an illustration of study interventions. Standard care can take place at anytime on Figure 1.

3.1.1 Screening Phase and Baseline Assessment

The "screening phase" will take place in triage or in a treatment area in the emergency department and will be considered to take place from when the patient arrives to the emergency department to when then patient completes their consent form, during the same visit.

Inclusion and exclusion criteria will be posted throughout the emergency department.

Any staff member can notify a physician or advanced practice provider if a patient may meet study criteria, once that has been determined, staff will notify a study research associate to ensure patient has all inclusion criteria and no exclusion criteria and then obtain informed consent.

The attending physician will ensure that each patient has capacity to participate in informed consent and will document this on the patients consent form.

3.1.2 Study Intervention

The study intervention will be the administration of either lidocaine or hydromorphone and will take place during the "intervention phase" of the study. Both drugs will be given as a drip over 5 minutes. This is for the purpose of blinding, as hydromorphone is generally given as a push dose or very slowly, and lidocaine is safest when given over a slow infusion, typically 5-15 minutes. Giving hydromorphone over 5 minutes will increase its safety as this will decrease its chances of causing respiratory depression or euphoria. Lidocaine will be dosed at 2 mg/kg of patients recorded weight, hydromorphone will be dosed at 1 mg. Intravenous hydromorphone meets standard of care for severe pain in the emergency department. Intravenous lidocaine has been shown to be effective for severe pain however it would not be considered standard of care and is not FDA approved for treating pain (when administered intravenously).

3.1.3 Follow-up

The “follow up phase” will take place 7 days after administration of study drug and will be completed by a study research associate via phone call.

3.2 Allocation to Groups and Blinding

Prior to the initiation of the study, a list will be generated which will randomly assign 187 patients to either lidocaine or hydromorphone in a roughly 50/50 distribution. This list will be generated by someone not involved with the study and will be given to the research pharmacists. Patients will be randomized by the research pharmacist in accordance with the list.

Ultimately research pharmacists will give the study drug to a nurse in a bag of saline. The only identifying information on the bag will be a standardized label as follows

Header (**INVESTIGATIONAL MED**), Patient name, age, medical record number, location, tube number, order number, due time and date, drug name (INV lidocaine or hydromorphone in NaCL 0.9% 100 ml IVPB), intravenous, once, 100ml, infuse over: 5 minutes, time label printed, signature for preparer and checker, expiration, and “Caution: New Drug - Limited by Federal (or United States) law to investigational use”

3.3 Study Duration, Enrollment and Number of Sites

3.3.1 Duration of Study Participation

Participants will participate for 7 days, however that participation on day 1 is limited to 180 minutes after administration of study drug. Patients will then be asked to participate 7 days after administration of study drug, via a phone call, conducted by a study research associate.

3.3.2 Total Number of Study Sites/Total Number of Subjects Projected

The study will only be conducted in the Hennepin County Medical Center Emergency Department. Recruitment will stop after 187 patients have been consented.

3.4 Study Population

3.4.1 Use of Vulnerable Populations and Patients Who Opt Out of Research

No vulnerable patients will be considered eligible for this study. Neonates and children do not meet the minimum age of inclusion criteria. Pregnant women and fetuses will be excluded by positive pregnancy test (urine or blood). Only patients who have capacity to consent, ultimately determined and documented by the attending physician, can participate so patients with diminished capacity to consent will be excluded. Adult prisoners will not be approached for

eligibility. Any patient who opts out of research will not be included in this study as consent is required for study participation.

3.5 Inclusion and Exclusion Criteria

3.5.1 Inclusion Criteria

- 1) Adults at least 18 years of age but no more than 64
- 2) Abdominal (abdomen or flank) pain severe enough to warrant intravenous narcotics (as determined by the clinical team), for a duration of 7 days or less

3.5.2 Exclusion Criteria

- 1) Pregnant or breast feeding
- 2) Prolonged cardiac intervals on EKG (QTc duration > 0.5s, QRS duration > 0.12s, PR interval <0.12s or > 0.2s) or any cardiac history, defined as “cardiac arrhythmias, heart blocks, congestive heart failure, or known cardiovascular disease, or deemed to have clinical signs of heart failure on physical exam”. This EKG must be from the same day.
- 3) Renal impairment, defined as CKD > 2 (CKD 1 and 2 are acceptable), as verified by blood work in the preceding 12 months, or evidence of renal impairment by history and/or physical examination
- 4) Liver impairment, defined as Childs-Pugh B or greater, as verified by blood work in the preceding 12 months, or evidence of liver disease by history and/or physical exam
- 5) Hemodynamically unstable (as determined by attending physician)
- 6) Allergy to lidocaine or hydromorphone
- 7) Self-report of any opioid use within the previous 7 days
- 8) Diagnosis of chronic pain, defined as using any pain medication more days than not in the previous 30 days
- 9) Inability to provide informed consent
- 10) Not wanting to participate in research
- 11) History of seizures

Subjects that do not meet all of the enrollment criteria may not be enrolled. Any violations of these criteria must be reported in accordance with IRB Policies and Procedures.

4 STUDY PROCEDURES

4.1 Screening Visit and Baseline Assessment

Please refer to Table 1 for specific timing of procedures

- Screen for meeting inclusion and exclusion criteria
- Obtaining informed consent (including attending physician certifying the patient is appropriately able to give consent)
- Recording of patients demographics and medical history (age, gender, history of diabetes, high blood pressure, high cholesterol, heart disease defined as coronary artery disease or congestive heart failure, seizures), history and physical exam to exclude any clinical evidence of acute cardiac, renal or liver disease
- Pregnancy test
- EKG

4.2 Study Intervention

4.2.1 Time Zero

- Pain score (1-10)
- Patient placed on monitor
- Vital signs recorded (heart rate, respiratory rate, systolic blood pressure, diastolic blood pressure, pulse oximetry, source of oxygen)
- Study drug administered by patient's nurse (mixed by research pharmacist and sent to the nurse) over 5 minutes

4.2.2 15 minutes after the study drug was started (not after it finished), up to a 15 minute delay will be tolerated

- Pain score
- Vital Signs (same as above)
- Recording of any new symptoms (classified at this point as adverse events)
- Recording of sufficient pain relief (yes or no)
- Recording of any medications to treat adverse events (yes or no). If yes, document was medication was administered, why, and when.
- Recording on whether or not naloxone has been administered (yes or no)
- Recording of any change in disposition thought to be due to study drug (yes or no)
- Recording of any serious adverse event (yes or no)

4.2.3 30 minutes after the study drug was started (not after it finished), up to a 15 minute delay will be tolerated

- Pain score
- Vital Signs (same as above)
- Recording of any new symptoms (classified at this point as adverse events)
- Recording of sufficient pain relief (yes or no)
- Recording of any medications to treat adverse events (yes or no)
- Recording on whether or not naloxone has been administered (yes or no)
- Recording of change in disposition thought to be due to study drug (yes or no)
- Recording of any serious adverse event (yes or no)

4.2.4 60 minutes after the study drug was started (not after it finished), up to a 15 minute delay will be tolerated

- Pain score
- Vital Signs (same as above)
- Recording of any new symptoms (classified at this point as adverse events)
- Recording of sufficient pain relief (yes or no)
- Recording of any medications to treat adverse events (yes or no)
- Recording on whether or not naloxone has been administered (yes or no)
- Recording of change in disposition thought to be due to study drug (yes or no)
- Recording of any serious adverse event (yes or no)

4.2.5 90 minutes after the study drug was started (not after it finished), up to a 15 minute delay will be tolerated

- Pain score
- Vital Signs (same as above)
- Recording of any new symptoms (classified at this point as adverse events)
- Recording of sufficient pain relief (yes or no)

- Recording of any medications to treat adverse events (yes or no)
- Recording on whether or not naloxone has been administered (yes or no)
- Recording of change in disposition thought to be due to study drug (yes or no)
- Recording of any serious adverse event (yes or no)

4.2.6 120 minutes after the study drug was started (not after it finished), up to a 15 minute delay will be tolerated

- Pain score
- Vital Signs (same as above)
- Recording of any new symptoms (classified at this point as adverse events)
- Recording of sufficient pain relief (yes or no)
- Recording of any medications to treat adverse events (yes or no)
- Recording on whether or not naloxone has been administered (yes or no)
- Recording of change in disposition thought to be due to study drug (yes or no)
- Recording of any serious adverse event (yes or no)

4.2.7 150 minutes after the study drug was started (not after it finished), up to a 15 minute delay will be tolerated

- Pain score
- Vital Signs (same as above)
- Recording of any new symptoms (classified at this point as adverse events)
- Recording of sufficient pain relief (yes or no)
- Recording of any medications to treat adverse events (yes or no)
- Recording on whether or not naloxone has been administered (yes or no)
- Recording of change in disposition thought to be due to study drug (yes or no)
- Recording of any serious adverse event (yes or no)

4.2.8 180 minutes after the study drug was started (not after it finished), up to a 15 minute delay will be tolerated

- Pain score
- Vital Signs (same as above)
- Recording of any new symptoms (classified as this point as adverse events)
- Recording of sufficient pain relief (yes or no)
- Recording of any medications to treat adverse events (yes or no)
- Recording on whether or not naloxone has been administered (yes or no)
- Recording of change in disposition thought to be due to study drug (yes or no)
- Recording of any serious adverse event (yes or no)

